Further, correcting misperceptions about normative drinking patterns is thought to influence alcohol use in two ways. First, an individual compares their personal alcohol consumption to normative perception about what others actually do (e.g., how much the average adult drinks). Second, the person uses their perceptions about other alcohol use as a benchmark for their own consumption patterns (Borsari & Carrey, 2001). Heavy drinkers often associate with other heavy drinkers and thus have an inaccurate perception of how much most people drink. Thus, BAIs were developed to help reveal discrepancies (a key concept in motivational interviewing; Rollnick et al., 2008) between a person's normative perceptions of alcohol use and actual consumption among age- and gender-matched peers (Hester et al., 2005; Neighbors et al., 2004; Nye et al., 1999). By correcting misperceptions about normative peer drinking behavior, personal benchmarks of "normal" alcohol use are typically reduced which thereby reduce alcohol consumption (Neighbors et al., 2004). Thus, given that BAIs are directly based on the principles of MI, they are well-positioned to support our partners in the implementation of the Uniform Mental Health Services Handbook SUD treatment guidelines which specifies a need for increased access to MI-based counseling approaches in medical settings.

BAIs are effective for civilian populations and can be delivered using various mediums. BAIs result in significant reductions in alcohol consumption among civilian adults and college students (Fleming et al., 1997; Hester et al., 2005; Kaner et al., 2007; Kypri et al., 2004; Kypri et al., 2008; Butler & Correia, 2009; Neighbors et al., 2004), with some evidence suggesting they may also be effective in active duty military populations (Williams et al., 2009). BAIs have been used to good effect in a variety of clinical settings, including primary care and HCV clinics (Dieperink, et al., 2010). For example, Dieperink et al., evaluated a face-to-face BAI delivered by HCV clinic providers and found that it reduced alcohol consumption and improved rates of antiviral treatment eligibility in a small sample (N = 47) of HCV-positive Veterans. Despite these positive outcomes, face-to-face administration of BAIs is relatively resource

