Part III of the interview will collect data on CFIR domain C - intervention characteristics involved in the care process. Providers will be asked to give their perceptions on current guidelines for treating alcohol use in HCV clinics and availability of treatment options at their facility. For example, potential assessment domains include: (k) perceptions about existing guidelines (e.g., “What do you think about current guidelines for addressing alcohol consumption in your clinic?” and “How effective/ineffective do you feel these guidelines are in helping you address this issue in your patient population?”) and (l) perceptions about and availability of treatment options for alcohol use (e.g., “How do you feel about existing treatment options for your patients reporting active alcohol use?”). In addition, providers will be asked to provide their reactions to the following treatment options: brief physician advice, the VHA brief alcohol counseling performance measure, brief alcohol interventions (e.g., assessment and feedback [BAI]), and referral to specialty SUD care, which (along with responses to questions in Parts I-II) will inform the re-versioning of the web-based BAI.

Aim 2

Veteran participants will be randomized into the experimental condition or TAU. Participants in the experimental condition will receive a web-based BAI which follows the general approach that has proven to be effective in previous studies. The BAI consists of two components (a) a brief computerized assessment and (b) a personalized feedback report (also see section 5.1).

All participants will receive an assessment at baseline, and follow up at 3- and 6-months. The assessment consists of the following topics: demographics, liver disorder diagnosis and treatment eligibility, patient satisfaction, primary and secondary outcomes.

Assessment Instruments

(a) Demographics. Characteristic such as age, gender, and previous or current involvement with inpatient/outpatient VA (or non-VA) substance use disorder (SUD) treatment or mental health care programs will be collected from the patient and through administrative records (CPRS and CDW). We will also assess current (or past) participation in a self-help SUD program such as Alcoholics Anonymous. We will assess possible exposure to these various forms of substance abuse treatment during the three- and six-month follow up periods.

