After the interviews and transcriptions are complete, the study coordinator and [name] will begin developing two separate codebooks for patient and providers. Codebook development will be an iterative process. Codebooks will be initially developed based on close readings of 30% of patient (n = 9) and 40% (n = 4) of provider transcripts. Themes that emerge from the patient and provider interviews will be continuously integrated into their respective codebooks. We anticipate that the final set of themes will consist of both themes defined a priori and new themes that emerge from each set of interviews. Upon completion of the initial version of the codebooks, the study coordinator and [name] will discuss the application of the codebooks to each set of interviews. This process will involve practicing applying the codebooks to a single patient and provider interview. When agreement is reached, the study coordinator and [name] will code a random sample of 20% of patient (n = 6) and 20% of provider (n =2) interviews to establish inter rater reliability. Once reliability is established (80% agreement), we will proceed to code the remaining portion of the patient and provider transcripts. Throughout the coding process, the PI and [name] will regularly discuss emerging themes, changing conceptualizations of existing themes, and to prevent drift. They will also consult intermittently with the other Co-Is and consultants to discuss emerging themes and conceptualizations. After data coding is complete, data analysis will begin, focusing on the frequency of code occurrence (by participant and code) and patterns of code co-occurrence for each set of interviews.

Aim 2

Based on findings from prior studies of web-based BAIs with similar follow-up time

frames, we expect an average effect size of .35 to .40 (range is .15 to .67) on alcohol consumption outcomes in response to the web-based BAI (Kypri et al., 2004; Kypri et al., 2008; Neighbors et al., 2004). Assuming a power of 80% of detecting an effect size of .35, an alpha level of .05, a 2-tailed test, a correlation of .5 between repeated measures of an outcome variable, and a 20% attrition rate at 6 months, we estimate that we will need 170 individuals per condition at baseline for a total sample of 340 across both sites, with one half in the experimental condition and TAU condition at each site (i.e., n=85 per condition at Palo Alto, n=85 per condition at San Francisco).

Data Analysis

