Prior to any regression modeling, we will first examine the sample distributions of each outcome variable and predictor variable to help us identify any possible errors in the data (e.g. coding errors). One of the benefits of our proposed use of generalized linear mixed model (GLMM) regression analyses is that it can accommodate a variety of conditional distributions for each outcome variable. Given that we will randomly assign participants to each condition, we expect the two groups to be comparable on baseline demographics and outcome variables at baseline. Nevertheless, we will conduct independent groups t-tests or chi-square analyses to check for any differences between the two groups on demographic characteristics and baseline outcome assessments. If differences are found between groups on any variables, we will control for those variables in subsequent analyses. Next, we will use generalized linear mixed-model (GLMM) regression analyses to compare the two conditions on our primary and secondary outcomes (Raudenbush et al., 2001; Singer et al., 2003). The primary hypothesis is that the slope of drinking outcomes over 0 to 6 months for participants in the web-based BAI plus TAU condition will differ from the TAU only condition. We will use the repeated measures data to fit a model consisting of fixed-effect terms for time since randomization, the time by condition interaction, and the site main effect. Random intercepts will be included to account for possible correlation among repeated measurements due to patient-specific latent factors. We will examine further constraints on the covariance structure and choose the final model by assessing goodness-of-fit. We will also examine the distribution of the outcome variables and associated random error components, choose appropriate link and variance functions (McCullagh & Nelder, 1991), and review any outliers.

Examining Mediators and Moderators

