Prior studies show that the effectiveness of web-based BAIs is at least partly due to the correction of misperceptions about normative alcohol use (i.e., social norms; Borsari & Carey, 2001; Neighbors et al., 2004). Therefore, we will test whether changes in social norms (e.g., descriptive and injunctive norms) mediate the effect of the web-based BAI on alcohol consumption. Following the recommendation of Baron and Kenny (1986), we will conduct a series of analytic steps (using regression models) to determine mediation: (a) we will test the effect of both intervention conditions on alcohol consumption; (b) the effect of intervention conditions on social norms; (c) the effect of social norms on alcohol consumption controlling for intervention condition; and (d) the effect of intervention condition on alcohol consumption after controlling for social norms. In addition, we will examine potential moderators (e.g., severity of alcohol use, coping, psychological distress) that may impact the effectiveness of intervention condition on treatment outcome. This analysis will help us determine whether the effectiveness of the intervention(s) is impacted by these variables at baseline and over the course of each follow-up.

Missing Data Prevention, Detection, and Adjustment

We will make every effort to prevent missing data at each assessment by achieving as high a response rate as possible. Baseline data will be collected during an in-person interview and follow-up assessments will be conducted as telephone interviews by study site

coordinators who have been trained to cover all questions and obtain as complete data as possible while respecting the patient's right to not answer specific questions. Based on previous follow-up studies of SUD patients conducted at our Center, we do not expect rates of missing data on any one variable to be greater than 5% at each assessment over and above missing data due to attrition, nor do we expect missing data to be systematically related to certain outcome variables. Nevertheless, given our plan to use an intent-to-treat approach that includes all patients who are randomized in our GLMM regression models, we will use multiple imputation. Multiple imputation procedure yields more efficient, accurate, and reliable inferences than ad-hoc methods of handling missing data (such as list wise deletion or mean substitution) (Shafer, 1997 Shafer et al., 2002; Little & Rubin, 2002).

Formative Evaluation Data Analysis

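### The social-norms mediation regressions name neither baseline drinking nor baseline norms, so the norms-to-drinking estimate can be biased in a direction that depends on how the variables are scored

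*Combined protocol and SAP*

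**What the plan says.** The mediation plan is in section 5.6, Examining Mediators and Moderators. Its aim is: "we will test whether changes in social norms (e.g., descriptive and injunctive norms) mediate the effect of the web-based BAI on alcohol consumption". It then lists four Baron-Kenny regressions. Step (c) is "the effect of social norms on alcohol consumption controlling for intervention condition" and step (d) is "the effect of intervention condition on alcohol consumption after controlling for social norms". No other covariate is named. The steps do not say whether norms and drinking enter as follow-up values, as change scores or as repeated measures.

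Three other parts of the plan bear on this:

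- **Adjustment.** Section 5.6 has one rule for baseline variables: "If differences are found between groups on any variables, we will control for those variables in subsequent analyses". The main model has "fixed-effect terms for time since randomization, the time by condition interaction, and the site main effect".
- **Data.** Section 5.5 says "All participants will receive an assessment at baseline, and follow up at 3- and 6-months". That assessment covers the primary outcomes (30-day TLFB drinking) and the secondary outcomes, of which social norms is item (l). Both baseline values will therefore exist.
- **Background.** Section 2.0 says "Heavy drinkers often associate with other heavy drinkers and thus have an inaccurate perception of how much most people drink".

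**The concern.** Condition is randomised, so steps (a) and (b) compare like with like. Norms are not randomised. If heavier drinkers enter the trial with different norms, and both characteristics persist, drinking and norms will be associated at follow-up whether or not one acts on the other. Step (c), adjusted for condition alone, picks up that association. Step (d) inherits it, because its condition coefficient comes from the same regression.

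The imbalance rule cannot help. It is triggered by differences between arms, and this confounding is present when the arms are perfectly balanced.

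What is at stake is the trial's only planned test of how the intervention works. The answer could lean towards mediation, or away from it, according to a scoring choice the plan leaves open.

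**Working it through.** The plan gives no sample size, power or error rate for mediation, so there is no figure of its own to reproduce.

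**Inputs from the documents (section 5.6)**
- 170 per arm less 20% attrition: 170 × 0.80 = 136 completers per arm, 272 in all.
- Effect on drinking .35 SD, two-sided alpha .05.
- "a correlation of .5 between repeated measures of an outcome variable", used here for drinking.

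**Assumptions not in the documents**
- Baseline norms-drinking correlation r = .2, .4 or .6.
- Norms stability .5, and an intervention effect of .35 SD on norms.
- Follow-up residuals of norms and drinking independent, meaning no residual confounding.

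**1. Spurious step (c) coefficient when norms have no effect.** Both variables are standardised, so the variance of a change score is 1 + 1 − 2(.5) = 1. Within arm:
- Raw follow-up values: .5 × .5 × r = +.25r
- Change in norms only: .25r − .5r = −.25r
- Change in drinking only: .25r − .5r = −.25r
- Change in both: .25r − .5r − .5r + r = +.25r

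The size is .05, .10 or .15 for r = .2, .4 or .6, and zero at r = 0. Using change in both does not cure the bias here, and using change in only one reverses it.

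**2. How often step (c) is significant.** The standard error is about √((1 − b²)/269) ≈ .061, so z ≈ 0.82, 1.65 and 2.49. Then Φ(z − 1.96) + Φ(−z − 1.96) gives 13%, 38% and 70%. Simulation gives about 13%, 37% and 69%. With both baselines added it is 4–5%.

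**3. How often steps (a) to (c) all pass in the mediating direction.** Steps (a) and (b) each have z = .35 × √(136/2) = 2.89, a power of 82%. Treating the steps as nearly independent, .823² × (.127, .378, .702) = 9%, 26% and 48%. Simulation gives about 9%, 26% and 47% with raw scores. With change in norms alone this almost never happens, because the bias is negative. With both baselines added, steps (a) and (b) have z = .35/√.75 × √68 = 3.33, a power of 91.5%. Then .915² × .025 ≈ 2%.

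**4. Size of the false indirect effect, raw scores.** .35 × (.05, .10, .15) = .018, .035 and .053, which is 5%, 10% and 15% of the total effect of .35.

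**5. A real mediator: true coefficient .20, r = .4.** The result depends on how norms act.

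| Scoring | Follow-up norms level acts | Only the part not predicted by baseline acts |
|---|---|---|
| Raw | .25r + .20 = .30 | .25r + .15 = .25 |
| Change in norms only | −.25r + .10 = .00 | −.25r + .15 = .05 |
| Change in drinking only | −.25r + .20 = .10 | −.25r + .15 = .05 |
| Change in both | .25r + .10 = .20 | .25r + .15 = .25 |
| Raw plus both baselines | .20 | .20 |

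With change in norms only, an estimate of .00 to .05 leaves little chance of detection. The baseline-adjusted model has about 90% power.

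**6. Limit of the cure.** If the follow-up residuals correlate at .2 for some other reason and norms do nothing, the adjusted coefficient is .20. With a standard error near .06 it is significant in about 92% of trials.

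**The case against.** The strongest reply is that the four steps are a conceptual outline and that silence on covariates is not exclusion. In particular, mediation might be run in the repeated-measures model, where baseline drinking already enters as an outcome. That is a fair reading, but it does not remove the problem. Take baseline and one follow-up, with norms as a time-varying predictor and a random intercept. The within-person slope is .25r. The between-person slope is (r + .25r + 2 × .5r)/(1 + 1 + 2 × .5) = .75r. The fitted coefficient is a weighted average of the two, so it is still positive when norms do nothing.

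Other parts of the case against stand and limit the point:

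- A reader might take the 13% to 69% as the chance of falsely declaring mediation. It is not. It counts step (c) alone, in either direction. The chance through steps (a) to (c) is lower and also needs the intervention to shift norms.
- A reader might infer that the trial would report norm correction as the mechanism when it is not. The documents do not support that. The spurious indirect effect is modest under these assumptions. Apparent full mediation, with condition no longer significant in step (d), occurs in only about 1%, 6% and 11% (raw scores, r = .2, .4, .6).
- The Introduction's statement concerns beliefs about how much others drink. It says nothing about the 10-item injunctive measure, so the confounding is documented only for descriptive norms.
- Baseline adjustment should not be read as making step (c) unconfounded, as item 6 of the working shows.
- Hypotheses H1 to H3 contain no mediation hypothesis.

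**Conclusion.** The concern holds for a secondary mechanism analysis. As written, steps (c) and (d) leave the non-randomised path open to a baseline association that the protocol itself describes, and nothing else in the plan closes it. Its size is conditional. It vanishes if baseline norms and drinking are uncorrelated, and it grows with that correlation, which the documents do not give. Its sign depends on an unstated scoring choice: raw scores can suggest or overstate mediation, while change in norms alone can hide it.

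The adjusted error rate of 4–5% for step (c), and about 2% for the whole sequence, rests on there being no residual confounding. The randomised comparisons of drinking and the other outcomes are not affected.

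**What to change.** In section 5.6, Examining Mediators and Moderators, specify that:

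- each regression includes the baseline value of its own outcome;
- steps (c) and (d) include both baseline drinking (the same TLFB measure as the outcome) and baseline social norms (the matching descriptive or injunctive measure), besides condition and the randomisation strata (site and alcohol dependence);
- baseline adjustment reduces confounding but may not remove it, and the norms coefficient is read as causal only if nothing else confounds norms and drinking.

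Once both baselines are in the model, follow-up values and change scores give the same norms coefficient, so the open scoring choice stops mattering. The cost is a few sentences of plan text and a few degrees of freedom. No new data are needed.

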4.0 Resources and Personnel

This four year study will be based at two sites - the (a) VA Palo Alto Health Care System, VA HSR&D Center for Health Care Evaluation and Liver Clinic, and (b) San Francisco VA Medical Center, Liver Clinic. This study will also collaborate with the VA Women's Health Practice-Based Research Network to provide technical expertise relevant to

administrative functions (e.g., Central IRB) and enhance our team's ability to oversample for women and optimize retention of women participants in our study.

The PI, VAPAHCS and SFVAMC Co-I's, and study coordinators from each site will have access to protected health information. De-identified information will be utilized when possible in data analysis. Study coordinators at both sites, will be involved in **recruiting** subjects and obtaining **informed consent** for Aims 1 and 2 of the study. For Aim 1, study coordinators at both sites will **administer the interviews** with patients and providers. For Aim 2, the study coordinators at VAPAHCS and SFVAMC will **administer** the web-based BAI to Veterans randomized to the treatment condition at baseline, along with the assessment survey to all Veteran participants at baseline (in-person interview), and 3- and 6-months post-treatment (phone interview). **Data analysis** will be performed by the PI and Co-Is, and supported by the consultants and research staff as detailed below.

[name]., Principal Investigator

[name] will oversee all aspects of the proposed project in partnership with our partners, The VA Office of Mental Health Services, Office of Mental Health Operations (10N), and VA Office of Public Health. He will supervise study personnel; coordinate data collection protocols, staff training, develop study procedures; and take responsibility for data analysis and the dissemination of findings. He will also co-lead development of the qualitative interviews and protocol, and participate in conducting interviews with staff and patients. He will ensure that the study protocol and all human subjects and data security regulations are followed. Dr.

[name] will also be responsible for communicating and supporting our partners in interpreting the policy and health care implications of our study findings.

[name].; Co-Principal Investigator – not VA Palo Alto

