(c) Patient satisfaction. We will use a brief patient survey that we developed from our preliminary work to assess patients' satisfaction with both treatment conditions. This survey will ask patients to respond to a series of statements regarding their satisfaction with the interventions received (e.g., "I felt comfortable disclosing my alcohol use to a computer program"; "My provider helped me understand how alcohol use may worsen liver disorder(s)."). This assessment will be completed by patients upon completion of the baseline assessment (and upon completion of the web-based BAI for patients assigned to the experimental condition).

Primary Outcomes.

(d) Alcohol quantity and frequency. Reduction in alcohol use will be measured using the 30-day Time Line Follow-Back instrument (TLFB; Sobell & Sobell, 1992). The TLFB is a calendar that provides visual cues to aid persons in retrospective recall of drinking behavior. It uses "cues" (e.g., holidays, birthdays) to help a participant recall drinking behavior (e.g., frequency and quantity of alcohol use) and has been shown to be reliable and accurate when administered individually over the telephone (Sobell et al., 1996). Based on recommendations from the alcohol treatment literature we will assess the *(a) number of drinking days, (b) mean number of drinks per drinking day, and (c) percentage of heavy drinking days* in the prior 30 days as our primary outcomes (Dieperink et al., 2010; Gastfriend et al., 2007). These outcomes will be measured by comparing TLFB drinking data at baseline (30-days prior) to data collected at three- and six-month follow-up (30 days prior).

Secondary Outcomes.

(e) Consequences of alcohol use. The Short Index of Problems (SIP-3months) is a brief, 15-item version of the Drinker Inventory of Consequences (DrInC) which assesses alcohol-related problems over the prior 3-months (Woolard et al., 2004). The SIP has sound psychometric properties (Kenna et al., 2005).

(f) Symptoms of psychological distress. Symptoms of psychological distress will be measured using the Brief Symptoms Inventory (BSI). The BSI instrument provides an overview of a patient's symptoms and their intensity at a specific point in time (Derogatis & Melisaratos, 1983). The reliability, validity, and clinical utility of the BSI instrument are well-established.

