(l) Social norms. Two questions will assess perceived quantity and frequency of alcohol consumption among participants' peers (i.e., descriptive norms, e.g., "How many drinks on one occasion do men/women your age consume?" [frequency]), while a 10-item measure will be used to assess concerns about harmful alcohol use (injunctive norms; Williams et al., 2009).

(m) Mini International Neuropsychiatric Interview (MINI). Section J, Alcohol Abuse and Dependence will measure the level of alcohol consumption over the past 30 days among participants. This is a 12-item assessment, with items rated from 0 (not at all) to 4 (extremely). This questionnaire will assess the presence of an alcohol use disorder (AUD) among participants.

Formative Evaluation Plan

We will utilize a well-established formative evaluation protocol that will include two site visits (to each study site) and interviews with staff (at each site) at three-month post initial implementation (e.g., Curran et al., 2008).

At the first site visit study staff will spend a day in each clinic reading program policy manuals and meeting with clinic directors. The latter will provide an opportunity to pose more focused questions on clinic policies (especially related to screening and treating current alcohol use). The meetings will be used to gauge clinic directors' support for the project as initial implementation will occur approximately one-year after funding notification. Therefore, it will be important to reassess clinic directors' current attitudes and beliefs, and answer any questions on the implementation process. When necessary we will provide brief, evidence summaries on the effectiveness of web-based BAIs and advocate VA practice guidelines for screening and treating alcohol use or misuse when appropriate.

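### The mediation steps have no rule for combining them, no interval for the indirect effect and no named visits, and the moderator sentence can be read as using follow-up values

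*Combined protocol and SAP*

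**What the plan says.** Section 5.6 (Data Analysis, Examining Mediators and Moderators) intends to "test whether changes in social norms (e.g., descriptive and injunctive norms) mediate the effect of the web-based BAI on alcohol consumption". To do so, "we will conduct a series of analytic steps (using regression models) to determine mediation". The steps are the effects of (a) condition on drinking, (b) condition on norms, (c) norms on drinking given condition, and (d) condition on drinking given norms. The text stops at (d).

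For moderators it names severity of alcohol use, coping and psychological distress as examples, and says the analysis will show whether "the effectiveness of the intervention(s) is impacted by these variables at baseline and over the course of each follow-up".

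Timing has to be pieced together from other sections:
- Section 5.5, Aim 2: "All participants will receive an assessment at baseline, and follow up at 3- and 6-months".
- Section 5.5, (l) Social norms, listed among the secondary outcomes: "Two questions will assess perceived quantity and frequency of alcohol consumption among" the participants' peers, plus a 10-item measure of injunctive norms.
- Section 5.5, Primary Outcomes: baseline drinking is compared with "data collected at three- and six-month follow-up (30 days prior"), so each drinking measure looks back 30 days from the visit.
- Section 4.0: coordinators administer "the web-based BAI to Veterans randomized to the treatment condition at baseline".

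The primary analysis in section 5.6 is a generalized linear mixed model (GLMM) in which the team will "choose appropriate link and variance functions". The outcome scale of the mediation models is therefore also open.

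**The concern.** These analyses are meant to say how the web-based intervention works and for whom. Four matters are left open, and each can change the answer.

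1. **Decision rule.** Steps (b) and (c) could serve together as a joint test, but the plan does not say so. It also does not say whether step (a) must be significant first.
2. **Size.** No estimate or interval for the indirect effect is planned, so a reader would learn which steps were significant but not how much of the effect runs through norms.
3. **Visits.** Changes in norms could mean baseline to 3 months or baseline to 6 months, paired with drinking at either visit. If norms and drinking come from the same visit, the drinking period precedes the norms answer, and people who drink less and then see peers as drinking less would look like mediation. The intervention is given at baseline, so no scheduled norms measure after it precedes the 3-month drinking period.
4. **Moderators.** Under one reading the moderator values are baseline values and the effect is followed over visits. Under the other they are taken at each follow-up, after treatment may have changed them. Psychological distress is itself an H2 outcome (section 3.0).

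**Working it through.** **Inputs.** Section 5.6 gives 170 per arm, 20% attrition, two-sided alpha .05, a planned effect of .35 and a range of .15 to .67. Completers: 170 x 0.8 = 136 per arm. The documents give no path values, so every path value below is an assumption.

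**The plan's own figure.** The only one is the sample size for the main comparison. n = 2(1.96 + 0.84)^2 / 0.35^2 gives 129 per arm, and 129 / 0.8 = 161.25, so 162. The stated 170 is slightly conservative. Nothing is stated for mediation or moderation.

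**Power of one step.** For a standardised difference d between arms, z = d x sqrt(136/2) = 8.246d, and power is about Phi(z - 1.96).
- Step (a): d = .35 gives z = 2.89, power 82%; d = .15 gives z = 1.24, power 24%.
- Step (b): norms shifts of .15, .20, .30, .375 and .50 give 24%, 38%, 70%, 87% and 98%.
- With 272 people, step (c) is close to certain for a norms-to-drinking path of .3 or more. The joint test of (b) and (c) then has about the power of (b).

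**Requiring step (a).** Norms = shift x arm + noise; drinking = direct x arm + path x norms + noise; within-arm SD 1. Simulated detection:

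| Total effect | Shift, path, direct | (a) required | (a) not required |
|---|---|---|---|
| .15 | about .15 shift | 9% | 24% |
| .15 | .20, .3, .09 | 13% | 38% |
| .15 | .30, .5, 0 | 22% | 70% |
| .15 | .375, .4, 0 | 23% | 87% |
| .15 | .50, .3, 0 | 24% | 98% |
| .35 | .20, .3, .29 | 34% | 38% |
| .35 | .35, .3, .245 | 70% | 83% |
| .35 | .50, .3, .20 | 81% | 99% |

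Repeat runs move these by a point or two. At .35 the loss is about 4 points (38 - 34) to 18 points (99 - 81).

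**Same-visit reverse causation.** Let the intervention lower drinking by .35 SD and let norms merely follow drinking with link k, so that nothing is mediated. The arm difference in norms is .35k: .105, .175 and .245 for k = .3, .5 and .7. Step (b) then has z = 0.87, 1.44 and 2.02, or power 14%, 30% and 52%, and step (c) is nearly always significant. Simulation of steps (a) to (c) gives false passes of about 12-13%, 28-29% and 49%. Dropping step (a) leaves about 14%, 30% and 51%. The missing visits are thus a separate gap from the missing interval.

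**Follow-up moderators, no true effect modification.**
- Where treatment only shifts the mean of the moderator (by .20 to .35, with moderator-drinking correlation .3 to .7), the condition coefficient moves from -.35 to between -.29 and -.11, and false interactions stay near 5%.
- Where the arm also changes the link between follow-up moderator and drinking, false interactions rise. In one model, drinking = -.35x + .3W0 + .6U + noise and follow-up moderator = .5W0 + (.5 + g x)U - .2x + noise (x = arm, W0 = baseline moderator, U = a shared factor). With g = 0, -.25 and -.5, the interaction is significant in 5%, 10% and 53% of trials. Baseline values give about 5% throughout.

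**The case against.** The strongest reply is that these are secondary analyses and that a competent analyst would choose sensibly. It is right that they lie outside H1 to H3 and leave the primary comparison untouched. It does not close the gap: with three drinking outcomes and at least two norm types there are at least 3 x 2 = 6 results, each with visits and decision rule left to be chosen after the data are seen.

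Several stronger readings are tempting and are not supported.
- A reader might infer that the plan contains no test of mediation at all. Steps (b) and (c) together form a joint-significance test; what is missing is the rule, the estimate and the interval.
- A reader might infer that step (a) is a gate, or that a gate would always be costly. The plan does not say it is one. With a small norms shift, mediation is mostly missed either way (38% without the gate at a shift of .20).
- A reader might infer that follow-up moderators are planned. The sentence also allows baseline values with the effect followed over visits. Section 5.1 (Method for Randomization) stratifies on baseline severity, and section 5.3 has other mental health care documented at baseline. Neither settles the sentence for coping or distress.
- A reader might infer that follow-up values necessarily lose power. That assumes the baseline value is the true modifier; if the concurrent value is, the order reverses. The sound objection is bias from conditioning on something treatment may change.
- A reader might infer that false interactions are always inflated, or never. They depend on whether the arm alters the moderator-drinking link.

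**Conclusion.** The concern holds as a gap in specification. The mediation text leaves open the decision rule, the role of step (a), the size of the indirect effect and the visits; the moderator sentence has two readings, one of which uses variables that treatment may change.

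Under the assumed paths, same-visit analysis would report mediation in roughly one trial in eight to one in two when none exists. A step (a) gate at the low end of the plan's effect range would leave detection at 9-24%. Follow-up moderators can pull the condition effect towards zero and, in some circumstances, raise false interactions above 5%. All of these sizes rest on assumed path values, 136 completers per arm and continuous outcomes. The ambiguity and the time order follow from the documents alone.

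It should be corrected because the cost is low, but it does not threaten the trial's main conclusion.

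**What to change.** Amend the mediator and moderator text in section 5.6 as follows.

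1. Define moderators as values measured before randomisation, tested as condition x moderator x time terms in the GLMM.
2. Report the indirect effect with a bootstrap 95% interval whether or not step (a) is significant. If the link is not the identity, report it on the outcome scale (days, drinks, percentage points).
3. Use 3-month norms and 6-month drinking, adjusted for baseline norms and baseline drinking. Report same-visit and 3-month results as association only, and state that reverse causation is not excluded. Adjustment for 3-month drinking can be added as an optional sensitivity analysis, not as a condition for any claim.
4. Label both analyses exploratory.

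The caveat in item 3 is needed because the lag alone is not protection. Under pure reverse causation the baseline-adjusted lagged interval still excluded zero in 4-11%, 27-41% and 64-70% of simulated trials at links of .3, .5 and .7. Adding 3-month drinking cut this to 0-4%, or 7-23% at a link of .7 if drinking is measured with reliability .8.

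**Cost.** No new data: SAP text, and programming for the bootstrap (alongside the multiple imputation already planned) and for outcome-scale effects. The main downside is that a lagged analysis can miss mediation that is complete by 3 months. This is worst once 3-month drinking is adjusted for: in one assumed case detection fell from 99% to 5%. For that reason the adjustment should stay a sensitivity analysis, and a null result there should not be read as evidence against mediation.
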